To determine whether or not use of the LiDCOplus cardiac output monitor results in an estimate of a patient's response to a fluid challenge which is significantly different to that simply obtained using standard measures of blood pressure, heart rate and limb circulation.
- **Secondary endpoints**
[None]

Methodology

A patient undergoing fluid resuscitation guided by a LiDCOplus device will have a research data pro forma left at their bedside along with instructions on how to complete it. When a patient is given a fluid challenge (the fast intravenous administration of 250ml of Hartmann's solution) as part of their routine management, a number of additional actions will take place. The screen of the LiDCOplus will be covered up initially and baseline heart rate, blood pressure and subjective assessment of limb circulation will be recorded on the proforma. After the fluid challenge is administered the above observations will be recorded again and at this point an assessment of whether the patient is "responsive" or "unresponsive" will be made. The LiDCOplus screen will then be uncovered and the change in stroke volume will be recorded (the cut off for being fluid responsive is a change of >10%). Finally, an overall decision regarding fluid responsiveness is made and recorded, along with the grade of decision maker (e.g. staff nurse or consultant).

This observational study will be performed according to the Research Governance Framework for Health and Community Care (Second edition, 2006).

Study Population

The study population will be a convenience sample as appropriate to the study type so the exact number of participants is not known as yet.

We aim to include all patients undergoing fluid resuscitation using a LiDCOplus cardiac output monitor in Glasgow Royal Infirmary Intensive Care Unit during the study period.

The researchers will regularly review the patients on the ICU to identify suitable participants.

Inclusion criteria

- Adult patients
- Admitted to Intensive Care Unit (ICU)
- Undergoing fluid resuscitation guided by fluid challenges
- Monitored by a LiDCOplus cardiac output monitor attached to an arterial line

Exclusion criteria

- Poor arterial line trace
- Moribund state
- Patient / relative refusal
- Contra-indication to fluid bolus

Identification of participants and consent

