4.1 Primary Outcome Measure

Proportion of decisions about fluid management changed by knowledge of the change in stroke volume post fluid challenge, as derived by LiDCO cardiac output monitor.

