4.2. Secondary Outcome Measure

None

Statistics and Data Analysis

As this is a descriptive study only descriptive statistics will be used, i.e. the proportion of patients deemed fluid-responsive by the use of LiDCOplus versus standard parameters alone and the proportion of fluid responsiveness decisions altered when the information from the LiDCOplus is taken into account.

STUDY CLOSURE / DEFINITION OF END OF TRIAL

The study will end when the planned sample size has been achieved.

Protocol Amendments

Any change in the study protocol will require an amendment. Any proposed protocol amendments will be initiated by the CI following discussion with the TSC and any required amendment forms will be submitted to the regulatory authority, ethics committee and sponsor. The CI and the TSC will liaise with study sponsor to determine whether an amendment is non-substantial or substantial. All amended versions of the protocol will be signed by the CI and Sponsor representative. Before the amended protocol can be implemented favourable opinion/approval must be sought from the original reviewing REC and Research and Development (R&D) office(s).

Ethics

The study will be carried out in accordance with the World Medical Association Declaration of Helsinki (1964) and its revisions (Tokyo [1975], Venice [1983], Hong Kong [1989], South Africa [1996] and Edinburgh[2000]).

Favourable ethical opinion will be sought from an appropriate REC before patients are entered into this study.

The CI will be responsible for updating the Ethics committee of any new information related to the study.

Finance and Indemnity

NHS employed researchers will be covered for negligent harm through the NHS CNORIS indemnity scheme. If you are a University employee you may need extra cover for non-negligent harm through your University. Please check this with your Research and Enterprise department.

The study is sponsored by NHS Greater Glasgow & Clyde. The sponsor will be liable for negligent harm caused by the design of the trial. NHS indemnity is provided under the Clinical Negligence and Other Risks Indemnity Scheme (CNORIS).

Publications

Study results whether, negative or positive, should be disseminated. Details of your plan for dissemination should be included here.

Reference

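### The planned LiDCOplus versus standard proportions are only margins of paired data, so disagreement between the stroke volume class and the clinical call is not reported; the primary outcome is unaffected

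*Protocol*

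**What the plan says.** The Methodology section of the Protocol records three classifications on the same challenge:

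- a responsive or unresponsive call made with the monitor screen covered;
- the change in stroke volume once the screen is uncovered, where "the cut off for being fluid responsive is a change of >10" per cent;
- a final judgement, in that "an overall decision regarding fluid responsiveness is made and recorded".

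Statistics and Data Analysis restricts the analysis to descriptive statistics and names two. The first is "the proportion of patients deemed fluid-responsive by the use of LiDCOplus versus standard parameters alone". The second is "the proportion of fluid responsiveness decisions altered when the information from the LiDCOplus is taken into account".

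The second corresponds to section 4.1, Primary Outcome Measure: "Proportion of decisions about fluid management changed by knowledge of the change in stroke volume post fluid challenge". The Primary Endpoint is worded differently. It asks whether the monitor leads to an estimate of a patient's "response to a fluid challenge which is significantly different to that simply obtained using standard measures of blood pressure" and the other bedside signs. The Background section says that no published study was found that tests the stroke volume change itself against clinical parameters, and that the present study proposes to do so.

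**The concern.** The first statistic takes paired classifications and reports each one's total separately. A challenge called responsive at the bedside but not by LiDCOplus offsets one where the reverse holds. Two similar percentages therefore say little about whether the two assessments agree on individual challenges, which is what the Primary Endpoint and the Background section ask.

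The second statistic is paired, but it compares the covered-screen call with the overall decision. If staff see a stroke volume result that conflicts with their call and keep the call, nothing is counted as altered. That kind of disagreement is then invisible in the planned output. At stake is a supporting result: how often, and in which direction, the monitor and the bedside assessment differ. The Protocol says its findings may encourage or reduce use of the device, so the direction matters to a reader.

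**Working it through.** The Protocol gives no sample size, responder rate or agreement figure, so there is nothing to reproduce. The 100 challenges and the rates below are assumptions for illustration.

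**Notation.** For n challenges, let a = responsive by both, b = by standard assessment only, c = by LiDCOplus only, d = by neither.

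- Standard proportion p1 = (a+b)/n; LiDCOplus proportion p2 = (a+c)/n.
- Net difference p2 − p1 = (c−b)/n.
- Disagreement = (b+c)/n.
- For given margins, disagreement can lie anywhere from |p1−p2| to min(p1+p2, 2−p1−p2).
- Kappa = (po−pe)/(1−pe), with po = (a+d)/n and pe = p1·p2 + (1−p1)(1−p2).

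**Same margins, different agreement (n = 100).**

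| p1 / p2 | a, b, c, d | Disagreement | Kappa |
|---|---|---|---|
| 50% / 50% | 50, 0, 0, 50 | 0% | 1 |
| 50% / 50% | 25, 25, 25, 25 | 50% | 0 |
| 50% / 50% | 0, 50, 50, 0 | 100% | −1 |
| 60% / 60% | 60, 0, 0, 40 | 0% | 1 |
| 60% / 60% | 36, 24, 24, 16 | 48% | 0 |
| 30% / 30% | 30, 0, 0, 70 | 0% | 1 |
| 30% / 30% | 9, 21, 21, 49 | 42% | 0 |
| 50% / 60% | 50, 0, 10, 40 | 10% | 0.8 |
| 50% / 60% | 30, 20, 30, 20 | 50% | 0 |

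The maximum is 80% at 60%/60% and 60% at 30%/30%. At 50%/60% the range is |0.5−0.6| = 10% to min(1.1, 0.9) = 90%, so perfect agreement is excluded once the margins differ.

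**Does the second statistic fill the gap?** That depends on what the LiDCOplus proportion means.

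*Reading 1: the overall decision.* Both statistics then describe the same table. The margins give c−b and the proportion altered gives b+c. For example, 50%, 60% and 50% altered give b = (0.5+0.5−0.6)/2 = 20%, c = (0.5−0.5+0.6)/2 = 30% and a = 50%−20% = 30%. The table is recovered in full, provided both statistics are counted per challenge. The first is worded per patient and the second per decision. On this reading, however, neither statistic uses the >10% class, so stroke volume against clinical assessment is not reported.

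*Reading 2: the >10% stroke volume class.* The margins then belong to the covered-screen call by stroke volume class table, while the proportion altered belongs to the covered-screen call by overall decision table. Suppose 50% of challenges are discordant, staff override 80% of those, and no decision changes where the two agree. The proportion altered is 0.50 × (1−0.80) = 10%. The report would read 50% versus 50% with 10% altered, and the 50% disagreement would not appear.

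**The case against.** The strongest reply is that the same sentence of the plan contains a paired measure that does not cancel, and that this measure is the primary outcome. That stands. It is also fair to say that the Study Hypothesis speaks of a judgement made with information from the monitor, which favours Reading 1, where the table is recoverable. Against that, the Background section and the stated >10% cut-off point to the stroke volume class. The text does not settle it, and Reading 1 leaves the Background comparison without any statistic.

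A reader might infer that the study could publish equal percentages, conclude there is no difference, and so answer its endpoint wrongly. The document does not support this. It attaches no test or decision rule to the two proportions, nowhere says that equal percentages will be read as agreement, and reports the proportion altered beside them. Perfect agreement and 50% disagreement at equal margins would give identical full reports only on Reading 2, and only if staff overrode every discordant result; any change acted on would separate them.

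It might also be said that the two proportions should go. They are legitimate descriptive results and are the margins of the table proposed here, so they should stay. Nor can the gap be left to a separate analysis plan with confidence: the Protocol's title says that the plan is included, and the point concerns a statistic the document states.

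**Conclusion.** The point holds in a limited form. The primary outcome is paired and unaffected. The other planned statistic shows only a net difference, its LiDCOplus side is undefined, and on both readings the plan omits how often the stroke volume class and the covered-screen call disagree. With assumed margins of 50% and 50%, that disagreement could be anything from 0% to 100%, with 50% the level expected by chance; with 50% and 60%, it is between 10% and 90%. These ranges rest on assumed rates, since the Protocol gives none. The weakness is in a supporting result and is worth correcting because the correction is nearly free.

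**What to change.** In Statistics and Data Analysis:

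1. State that the LiDCOplus proportion means the >10% stroke volume class.
2. State that the counts are per challenge, and keep the two proportions as margins.
3. Add the 2x2 table of covered-screen call by stroke volume class, with the proportion discordant and both off-diagonal cells.
4. Add the same table for covered-screen call by overall decision.
5. Label both tables as supporting results beside the unchanged primary outcome.

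The cost is a sentence or two of text. Every item is already on the pro forma, so no new data or patients are needed.

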Study Protocol **(including Statistical Analysis plan)**

Title

- Does the use of LiDCOplus alter decision-making in fluid prescription during resuscitation in the Intensive Care Unit?
- Or Use of LiDCOplus in Fluid Resuscitation Decision-Making

Introduction

- Rationale

Unwell patients in the intensive care unit (ICU) often need supplementary fluids to be given into the bloodstream through a drip in a vein (venous cannula), however too much fluid can be harmful. It can sometimes be difficult to tell whether or not a patient will benefit from extra fluids so they are given a "fluid challenge", whereby a small volume of fluid is given quickly into the cannula and the change in their status is noted. If the patient's condition improves, this suggests that the patient is "fluid responsive" and needs more fluid.

A LiDCOplus cardiac output monitor is a device used in the ICU to estimate the amount of blood ejected from the heart on each heartbeat using pressure readings obtained from a tube placed in one of the patient's arteries (arterial line).

We aim to determine whether or not the use of this device called makes a difference to the judgement of "fluid responsiveness" when the patient is given a fluid challenge when compared to simply using measurements of pulse and blood pressure and assessing the circulation in the patient's limbs. This will allow us to determine whether or not the LiDCOplus cardiac output monitor alters the decisions made by doctors and nurses about how much fluid to give their patients and hence if it is of any benefit.

- Background information including literature review

In the published literature there are multiple studies using the LiDCOplus-derived change in stroke volume as a gold standard of fluid responsiveness against other measures such as stroke volume variation and pulse pressure variation^{1,2}. However there do not seem to be any studies evaluating the change in stroke volume itself as a measure of fluid responsiveness against clinical parameters, as proposed in the current study.

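### Does the proportion of altered calls need to be split by whether each change moved toward or away from the monitor's reading?

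*Protocol*

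**What the plan says.** The protocol's title page describes the document as "including Statistical Analysis plan", so its Statistics and Data Analysis section can fairly be read as the plan.

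- **Question.** The Study Hypothesis and the Primary Endpoint both ask whether the judgement of response to a fluid challenge differs once LiDCOplus information is available, compared with standard bedside measures.
- **Outcome.** Section 4.1 defines it as "Proportion of decisions about fluid management changed by knowledge of the change in stroke volume post fluid challenge". Section 4.2 lists no secondary outcome.
- **Sequence.** Under Methodology the screen is covered first. The first call comes after the challenge, introduced by the words "at this point an assessment of whether the patient is", with two possible labels. Staff then uncover the screen and note the reading: "the change in stroke volume will be recorded (the cut off for being fluid responsive is a change of >10", a percentage. The closing step is a second call, made with bedside signs and reading both in view: "Finally, an overall decision regarding fluid responsiveness is made and recorded".
- **Analysis.** Statistics and Data Analysis confines itself to descriptive statistics and names two. The one that carries the primary outcome is "the proportion of fluid responsiveness decisions altered when the information from the LiDCOplus is taken into account". The other, listed before it, compares two margins: "the proportion of patients deemed fluid-responsive by the use of LiDCOplus versus standard parameters alone".

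**The concern.** Section 4.1 uses causal wording: the decisions counted are those "changed by knowledge of the change in stroke volume". A reader may therefore expect the report to show that changed calls went where the reading pointed. The planned figures do not show this. One is a total with no direction, the others are separate proportions, and none ties a changed call to the reading seen in the same challenge.

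The protocol's Rationale and its section on potential risk and benefits say that the results bear on whether the device is of use and may raise or reduce its use. If staff followed the monitor in one study and moved against it in another, the same proportion altered would seem to mean two different things. The items needed to tell them apart (first call, reading, final call) are all produced at the bedside, so the gap looks both real and cheap to close.

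**Working it through.** The protocol states no sample size, error rate or expected proportion, so there is no planned figure to reproduce. All counts and rates below are assumptions used to test the logic.

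**Step 1. Do the planned figures leave direction open?** Take 100 challenges, classified by first call (R responsive, U unresponsive) and reading (+ above the cut-off, − not):

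| First call / reading | Challenges | Altered in table X | Altered in table Y |
|---|---|---|---|
| R / + | 35 | 0 | 5 |
| R / − | 15 | 5 | 0 |
| U / + | 15 | 5 | 0 |
| U / − | 35 | 0 | 5 |

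- Responsive at first call: 35 + 15 = 50 in both.
- Reading above the cut-off: 35 + 15 = 50 in both.
- Responsive at final call: 50 − 5 + 5 = 50 in both.
- Altered: 5 + 5 = 10 of 100 in both.
- Toward the reading, out of the 15 + 15 = 30 discordant challenges: X 10/30 = 33.3%, Y 0/30.
- Away from the reading, out of the 35 + 35 = 70 concordant challenges: X 0/70, Y 10/70 = 14.3%.

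The point is general. Over 324 combinations (first-call and reading proportions each from 0.1 to 0.9 in steps of 0.1, and 0.05, 0.1, 0.2 or 0.3 altered), given those three figures, the toward share could be anything from 0% to 100% in 320 and was never a single value. Adding the final-call proportion can narrow it in extreme cases: with first call 0.9, reading 0.1, final call 0.8 and altered 0.15, the range is 17% to 100%. So direction is indeed left open.

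**Step 2. Is direction what the study sets out to estimate?** The outcome is altered calls divided by all calls, and altered = toward + away. In X that is 10 + 0 = 10; in Y it is 0 + 10 = 10. The outcome is 10% in both, and the planned figure reports exactly that. The hypothesis and endpoint ask whether the judgement differs, and both tables answer this equally. The toward share measures adherence to the monitor, which the hypothesis, endpoint and section 4.1 do not ask about.

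**Step 3. What carries the causal wording?** The order of events does. Within a challenge, the first call is made with the screen covered and the final one after it is uncovered, so the planned new information between them is the reading. A change away from the reading's side of the cut-off is not thereby excluded from having been prompted by it: the protocol asks for an overall decision and does not oblige staff to follow the cut-off, and a reading close to it may unsettle a call in either direction.

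**Step 4. Would a direction table settle attribution?** Suppose the device has no effect, 30% of challenges are discordant, and calls switch with probability 0.10 when discordant and *s* when concordant (discordant cases may simply be the harder ones). Per 100 challenges, toward = 30 × 0.10 = 3.0 and away = 70 × *s*.

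| *s* | Away | Altered | Toward share |
|---|---|---|---|
| 0.10 | 7.0 | 10.0 | 3.0/10.0 = 30% |
| 0.05 | 3.5 | 6.5 | 3.0/6.5 = 46% |
| 0.01 | 0.7 | 3.7 | 3.0/3.7 = 81% |

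A table in which four-fifths of changes go toward the reading can arise with no influence at all. Direction neither proves the attribution when favourable nor refutes it when not.

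**The case for a change.** The strongest case for the concern is that the protocol says it contains the analysis plan and introduces its two statistics as a definition rather than as examples. The table therefore cannot be presumed to sit in another document. It would cost nothing, a reader deciding about the device would want to see it, and committing to it beforehand guards against selective presentation.

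Part of this stands. The document should be judged as the plan, the algebra is right, and a cross-tabulation would be informative. But the restriction is to descriptive statistics, and a cross-tabulation of collected data is one, so nothing bars it. Omitting an extra descriptive table is no fault when the stated outcome is reported in full. Table Y also requires every altered call to come from someone who first agreed with the monitor, saw the agreeing reading and then switched against both; nothing in the protocol suggests this pattern.

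One limit of the design does remain: there is no repeat call with the screen still covered, so changes due merely to a second look are counted with the rest. A direction table would not separate them either, as the 81% example shows.

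**Conclusion.** The concern does not hold. The planned figures leave the direction of altered calls undetermined, but the hypothesis, endpoint and primary outcome do not ask for direction. Followed as written, the plan gives a sound descriptive answer to its own question, and the effect on the primary result is nil: 10% altered in both constructed tables. Splitting the altered calls would be an optional addition and would not supply proof of influence.

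This rests on three readings of the protocol:

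- The decision in section 4.1 is taken to be the responsiveness call, the only decision that Methodology asks staff to make.
- The covered-screen call is taken to be written down. Methodology says that it is made, and the outcome could not be computed without it.
- One denominator of challenges is used throughout the constructed tables. The protocol counts patients in one statistic and decisions in the other, which does not affect the conclusion here.

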There are two studies which compare outcomes in patients whose fluid therapy was guided by LiDCO vs controls. One was a pilot study of 21 severely burned adults which compared fluid therapy in patients with and without LiDCO monitoring and showed that the LiDCO group received significantly less fluid³. The other was a study on intra-operative patients undergoing surgical repair of fractured neck of femur under spinal anaesthetic⁴ and is not relevant to the critically unwell patients in the intensive care unit we wish to study.

There does, therefore, appear to be a lack of current evidence to address the research question and further research in to this area would be desirable.

- Potential risk and benefits

The results of this study should benefit patients in ICU by evaluating the usefulness of a piece of equipment used regularly to guide patient care. If it is shown to be useful, this may encourage its use in order to gain maximum benefit for patients. If it is shown not to be useful, this may lead to a reduction in its use and subsequent cost savings to ICU departments which can use the extra money to improve patient care in other areas.

There is minimal potential for direct benefit to patients as the research does not involve any change to their standard monitoring and treatment. However, there may be a benefit in the special attention paid to the patients' response to fluids e.g. minimising errors and picking up additional information from the patient's assessment.

There are minimal potential risks for research participants as their monitoring or treatment will not be affected apart from a very brief delay while the clinician fills out the research proforma by the bedside.

- Prior experience of intervention

The LiDCOplus device is widely used in the authors' intensive care unit to guide fluid therapy in patients requiring fluid resuscitation. It is thought that this allows administered fluid volumes to be tailored to maximize benefit and minimise harm to the patient it is not entirely clear from clinical experience whether or not this is the case.

- Study Hypothesis

The Null Hypothesis is there is no difference to the judgement of "fluid responsiveness" using information from a LiDCOplus monitor when a patient is given a fluid challenge, when compared to simply using standard clinical measurements of responsiveness.

Aim/Primary and Secondary Objectives

- **Primary Endpoint**

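### Does the end-of-study rule fail because it relies on a planned sample size that the protocol never states?

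*Protocol*

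**What the plan says.** The section on study closure and the end of the trial contains one rule: "The study will end when the planned sample size has been achieved". The Study Population section calls the sample a convenience sample, "so the exact number of participants is not known as yet", and aims to take in every eligible patient "in Glasgow Royal Infirmary Intensive Care Unit during the study period". That period has no dates or length. No number of patients or decisions appears anywhere.

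Section 4.1 defines the primary outcome as "Proportion of decisions about fluid management changed by knowledge of the change in stroke volume post fluid challenge", so its unit is the decision. The Statistics and Data Analysis section states "As this is a descriptive study only descriptive statistics will be used" and lists proportions. Under potential risks and benefits, the protocol says of the device: "If it is shown not to be useful, this may lead to a reduction in its use". The document's title line describes it as "including Statistical Analysis plan".

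**The concern.** The only explicit closure rule relies on a quantity that another section says is not yet known. Because the title line says the analysis plan is included, the text points to no other document that would hold the number. Read literally, nobody could tell when the closing condition had been met.

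What appears to be at stake is precision. The protocol foresees that an unfavourable result might reduce use of the device. A low proportion of changed decisions is good evidence for that only if enough decisions were recorded. With no number fixed and only proportions listed as output, a small sample might seem able to support a conclusion it cannot bear. Bias was not the worry: a stop chosen without reference to results does not distort the proportion.

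**Working it through.** **1. The sentences side by side.** The closure sentence presupposes a planned number. The Study Population sentence says the exact number is not yet known and gives convenience sampling as the reason. The same section then refers to a study period. The most natural reading is a time-bounded convenience sample, with a closure sentence that suits a different kind of study. The inconsistency is real. It would be a strict contradiction only if *planned* had to mean fixed when the protocol was written.

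**2. The plan's own figure.** There is none to reproduce. The protocol gives no sample size, expected proportion, significance level, power, precision target or threshold for usefulness. Every rate and count below is therefore an assumption, and decisions are treated as independent.

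**3. How precision depends on the count.** The exact (Clopper-Pearson) 95% interval for x changed decisions out of n runs from the 2.5% quantile of Beta(x, n − x + 1) to the 97.5% quantile of Beta(x + 1, n − x). With x = 0 the upper limit is 1 − 0.025^(1/n); for n = 20 this is 1 − 0.025^0.05 = 16.8%.

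| Decisions | Interval if 10% changed | Upper limit if none changed |
|---|---|---|
| 10 | 0.3% to 44.5% | 30.8% |
| 20 | 1.2% to 31.7% | 16.8% |
| 50 | 3.3% to 21.8% | 7.1% |
| 100 | 4.9% to 17.6% | 3.6% |

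This is the ordinary gain in precision with n. It does not show that this study would be small, because the protocol gives no accrual rate.

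**4. Whether a usefulness verdict depends on n.** Taking counts in tens, an observed 10% has its upper limit below 30%, 25%, 20% or 15% only from 30, 40, 70 or 210 decisions respectively. The required count moves sevenfold (210/30) with a threshold that the protocol does not set. The sentence on reduced use says only what may follow; it is neither an analysis rule nor a decision criterion.

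**5. What number could be written in.** For a 95% half-width h, n = 1.96² × p(1 − p)/h².

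- p = 0.10, h = 0.10: 3.84 × 0.09/0.01 = 34.6, so 35 decisions.
- p = 0.50, h = 0.10: 3.84 × 0.25/0.01 = 96.0, so 97.
- p = 0.10, h = 0.05: 3.84 × 0.09/0.0025 = 138.3, so 139.
- p = 0.50, h = 0.05: 3.84 × 0.25/0.0025 = 384.1, so 385.

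A target of 100 decisions would give a worst-case exact half-width of 10.2 points, but only for independent decisions. If each patient contributed 3 challenges with an assumed intraclass correlation of 0.3, the design effect would be 1 + (3 − 1) × 0.3 = 1.6, and 100 decisions would carry the information of about 100/1.6 = 62.5. No single figure follows from the documents.

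**The case for a change.** The strongest case for a change is that this is not an omitted power calculation, which a descriptive study can do without. It is a rule the protocol states and then undercuts. The study period cannot stand in for it, since it has no dates and the closure section does not mention it. The words *as yet* suggest a number to be set later, but no approximate figure is given and no step for setting one. The repair would cost a sentence in each place.

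The textual part of this stands: the rule has no value, and the intervals above are correct. The consequence does not stand. The worry that the listed output would hide a small sample is weak, because a descriptive proportion is ordinarily reported with its numerator and denominator and nothing in the analysis section prevents that. Adding an interval is a reporting detail that analysts supply as a matter of course.

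Nor would the available repairs secure what the concern wants. A chosen count such as 100 would be a preference with no accrual rate to show it is feasible, and it would still need a rule on repeat challenges in the same patient. A dated period would make the wording consistent but would guarantee no minimum precision.

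**Conclusion.** The mismatch between the closure sentence and the sample description is genuine but minor, a missing detail in a descriptive study. No change to the plan is needed. The primary proportion obtained under the plan as written would be sound at any achieved count, and its precision could be read from the denominator: at an assumed 10%, an upper limit of 31.7% from 20 decisions against 17.6% from 100. No stated figure is missed, because none is stated, and no listed analysis includes a test whose error rate could be affected.

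This rests on two assumptions: that the study stops for reasons unrelated to the accumulating proportion, and that the result is reported with its count. The intervals also assume independent decisions; positively correlated repeat challenges in one patient would widen them. A small achieved sample would limit how far an unfavourable result could be pressed, which is a matter for interpreting the report.
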